7.3.2. Analysis Methods

Actual values and changes from baseline will be summarized by treatment group at each scheduled timepoint, including the safety follow-up visit, the Day 28 final study visit and the last study visit.

A tabulation of the abnormalities per timepoint will be presented. This table will also show the number and percentage of subjects per abnormality, the number and percentage of subjects per treatment-emergent abnormality, and the cumulative number of subjects per treatment-emergent abnormality per post-baseline timepoint, including the safety follow-up visit, the Day 28 final study visit and the last study visit.

Additionally, a tabulation of the worst abnormality will be presented. This table will show the number and percentage of subjects per worst abnormality.

A cross-tabulation of the worst abnormality versus baseline will be presented per phase (treatment, follow-up and the combination treatment and follow-up phase). This table will also show the number and percentage of subjects per worst abnormality, the number and percentage of subjects per treatment-emergent worst abnormality, and the cumulative number of subjects per treatment-emergent abnormality.

Mean \pm SE graphs over time for the actual values and changes from baseline will be generated for all tests performed.

Vital signs data for subjects having at least one treatment-emergent abnormality will be listed.

7.4. Physical examinations

Abnormal physical examination results will be listed.

7.5. Electrocardiogram

PR duration, QT duration, QRS duration, Heart Rate and QTc intervals using Bazett's correction formula and Fridericia's correction formula will be investigated. QTc values will be used as reported, they will not be recalculated. If the ECG is performed in triplicate, then the mean of the non-missing ECG recordings will be used as the value for each specific parameter and timepoint.

7.5.1. Definitions

ECG abnormalities will be determined according to the boundaries defined in [Attachment 4](#).

An abnormality (based on normal ranges) will be considered treatment-emergent if it is worse than the baseline abnormality. If the baseline abnormality is missing, the abnormality is always considered as treatment-emergent. A shift from "abnormally low" at baseline to "abnormally high" post-baseline (or vice versa) is also treatment-emergent.

Assessments taken while the subject was not in a supine position will not be included in descriptive statistics but will be considered in determining worst case values.

7.5.2. Analysis Methods

Actual values and changes from baseline will be summarized by treatment group at each scheduled timepoint, including the safety follow-up visit, the Day 28 final study visit and the last study visit.

A tabulation of the abnormalities per timepoint will be presented. This table will also show the number and percentage of subjects per abnormality, the number and percentage of subjects per treatment-emergent abnormality, and the cumulative number of subjects per treatment-emergent abnormality per post-baseline timepoint, including the safety follow-up visit, the Day 28 final study visit and the last study visit.

A cross-tabulation of the worst abnormalities versus baseline will be presented per phase (treatment, follow-up and the combination treatment and follow-up phase). This table will also show the number and percentage of subjects per worst abnormality the number and percentage of subjects per treatment-emergent worst abnormality, and the cumulative number of subjects per treatment-emergent abnormality.

Mean \pm SE graphs over time for the actual values and changes from baseline will be generated for all tests performed.

A frequency tabulation of the QT/QTc change categories at Day 28, safety follow-up visit and last study visit versus baseline will be presented.

ECG data for subjects having at least one treatment-emergent abnormality will be listed.

8. RESISTANCE

8.1. Viral Phenotype

The pimodivir EC₅₀ and oseltamivir IC₅₀ with their fold change values will be analyzed at baseline and at all post-baseline visits with available data (FC = fold change in EC₅₀ (IC₅₀) value).

FC is calculated as the EC₅₀ (or IC₅₀) of the subject's influenza strain divided by the EC₅₀ (or IC₅₀) of a reference strain. If the patient EC₅₀ (or IC₅₀) is censored, the fold change value gets the same censor, eg, patient EC₅₀ = >20 nM, reference EC₅₀ = 4nM, Fold Change value >5.

The following output will be provided:

- Emerging phenotypic resistance: descriptive statistics for FC in EC₅₀ and IC₅₀ value for pimodivir and oseltamivir respectively at baseline and at all post-baseline visits with available data. The number (%) of subjects by treatment arm with censored phenotype data (by lower and upper bound) at baseline and at all post-baseline visits with available data will also be shown.
- Descriptive statistics for fold change ratio of all post-baseline visits with available data versus baseline including geometric mean and 95% CI.
- A listing showing viral load data together with phenotype data (EC₅₀, IC₅₀ and fold change values) per subject and influenza subtype for all available time points including screening/baseline.

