pimodivir was observed in 9 subjects. Seven of these 9 subjects also had emerging known PB2 position mutations, one subject had no genotypic data available, and one subject harbored T378S, a newly identified resistance mutation in PB2. No emergent-phenotypic resistance was observed in the combination arm. Virologic breakthrough was not observed in any of these subjects. Overall, a high correlation between the presence of PB2 mutations at positions of interest and the emergence of phenotypic resistance to pimodivir was observed. The PB2 mutation T378S was associated with high-level phenotypic resistance to pimodivir and represented a newly identified position of interest. The list of PB2 positions of interest was updated for subsequent analyses to contain the following 13 amino acid substitutions: Q306, F323, S324, F325, S337, H357, F363, K376, T378, F404, Q406, M431, and N510.

Resistance data from Study 63623872FLZ2002 are not yet available.

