A blinded Adjudication Committee (AC) will be established to adjudicate AEs on predefined criteria for complications (pulmonary versus extrapulmonary, major versus minor, as well as infectious versus non-infectious complications). The AC will receive data on AEs, including medical assessments (eg, chest X-ray results, lab results) and concomitant therapy of cases selected from the AEs. Details will be provided in an AC charter.

- Time to resolution of each of the 10 individual influenza-related symptoms as assessed by the PRO measure Flu-iiQTM. The resolution of each influenza-related symptom is defined as the beginning of the 24-hour period when the influenza symptom score is at most mild or at least back to previous level of symptom severity in case the subject reported the symptom as pre-existing.
- Time to return to daily activities as assessed by the subject.
- Time to resolution of fever. Resolution of fever is defined as a body temperature <37.0°C during a period of 24 hours without the use of antipyretics.
- All-cause mortality.
- PK parameters of pimodivir (ie, plasma concentration just prior to the beginning or at the end of a dosing interval [ $C_{\text{trough}}$ ],  $C_{\text{max}}$ ,  $t_{\text{max}}$ , and  $AUC_{12h}$ ), as determined by population PK analysis.
- The acceptability of the pimodivir formulation in adolescents, as measured by a taste and swallowability questionnaire.
- The emergence of viral resistance against pimodivir detected by genotyping and/or phenotyping.
- Time to viral negativity by qRT-PCR and viral culture.
- Viral load over time by qRT-PCR and viral culture.

Refer to Section 9, Study Evaluations, for evaluations related to endpoints.

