Influenza A subtype category	
 • A/H1N1 • A/H3N2 • Other 	
 - Efficacy (primary and two most important secondary endpoints only) - All viral kinetics - Viral phenotype - Viral genotype
Baseline polymorphism (based on influenza PB2 genotype)	Polymorphism on one or any of these amino-acid positions of interest: 
 • Q306 • F323 • S324 • F325 • S337 • H357 • F363 • K376 • T378 • F404 • Q406 • M431 • N510 	
 - Efficacy (primary endpoint only) - All viral kinetics - Viral phenotype - Viral genotype
Baseline resistance (based on influenza PB2 phenotype)	Based on fold change (FC) in EC ₅₀ for pimodivir: 
 • FC ≤4 • FC >4 	
 - Efficacy (primary endpoint only) - All viral kinetics - Viral phenotype - Viral genotype
Baseline Fever	Baseline (temperature ≥37.0°C) as recorded as part of the vital signs assessment	- Resolution of fever only
Influenza season	
 • Northern Hemisphere 2017/2018 • Southern Hemisphere 2018 • Northern Hemisphere 2018/2019 • Southern Hemisphere 2019 • Northern Hemisphere 2019/2020 • Southern Hemisphere 2020 and so on, to capture all enrolled subjects	
 - Efficacy (primary and two most important secondary endpoints only) - All viral kinetics - Viral phenotype - Viral genotype
Study period	
 • Pre interim (subjects enrolled for the interim analysis, ie randomized before or on February 28, 2020) • Post interim (subjects enrolled after the interim analysis, ie randomized after February 28, 2020) 	
 - Efficacy (primary and two most important secondary endpoints only) - Safety (AE summary, AEs and SAEs by MedDRA system organ class and preferred term, influenza-related complications, laboratory toxicity)
COVID-19 impacted	
 • Yes • No 	
 - Efficacy (primary and two most important secondary endpoints only) - Safety (AE summary, AEs and SAEs by MedDRA system organ class and preferred term, influenza-related complications, laboratory toxicity)

Influenza season is defined as follow:

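### SAP 8.1 never counts subjects whose pimodivir fold change rises above 4, so its tables give no per-arm incidence for the phenotypic part of the resistance endpoint

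*SAP*

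**What the plan says.** Protocol 2.1.2 lists as a secondary endpoint "The emergence of viral resistance against pimodivir detected by genotyping and/or phenotyping". Protocol 11.5 says that emerging mutations (by incidence) and changes in susceptibility (by EC50 fold change) will be described and compared between arms.

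SAP 8.1 plans these phenotype outputs:
- "Emerging phenotypic resistance: descriptive statistics for FC in" EC50 (pimodivir) and IC50 (oseltamivir), at baseline and at each post-baseline visit with data;
- the number and percentage by arm with lower- or upper-censored phenotype values at those visits;
- "Descriptive statistics for fold change ratio of all post-baseline visits with available data versus baseline including geometric mean and 95% CI";
- a per-subject listing that sets EC50, IC50 and FC next to viral load.

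On censoring, SAP 8.1 says that when the subject's EC50 or IC50 "is censored, the fold change value gets the same censor". It does not say how such a value enters a mean or geometric mean.

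The cut-off of FC above 4 appears in two places, both for baseline: the Phase 2b definition in Protocol 1.1 (Resistance) and the baseline-resistance subgroup in SAP 2.3, Table 6. For genotype, SAP 8.2 defines a treatment-emerging mutation and tabulates its frequency.

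**The concern.** Emergence is something that happens to individual subjects, usually a few. The natural summary is how many subjects out of how many, by arm. SAP 8.2 does this for mutations, and Phase 2b reported its phenotypic result the same way: emergent resistance to "pimodivir was observed in 9 subjects".

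SAP 8.1 instead summarises the distribution of FC. A median or geometric mean describes the typical isolate and is insensitive to a small resistant minority. The trial's phenotype tables could not be set beside the Phase 2b count, and the two arms could not be compared on incidence. The split by standard of care (SOC) matters too. Phase 2b saw no emergent phenotypic resistance in the oseltamivir combination arm, while SOC here may be supportive care only.

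**Working it through.** **Inputs**
- SAP 8.1 worked example: subject EC50 above 20 nM, reference EC50 4 nM.
- Protocol 1.1 (Resistance): 9 subjects with emergent phenotypic resistance; full analysis set 223; baseline phenotype available for 180; 57-fold loss of sensitivity in vitro for PB2 M431I.
- Protocol 1.4.4: 147 Phase 2b subjects treated with 600 mg bid, with or without oseltamivir.
- Protocol 11.3: 600 analysable subjects, so 300 per arm.
- Assumed: resistant isolates rise by a factor F of 5, 10 or 57, and all others are unchanged.

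**1. The plan's own figures reproduce.** FC = 20/4 = 5, so the example is FC above 5, as stated. 180/223 = 81%, also as stated.

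**2. Plausible rate.** 9/223 = 4.0% (exact 95% CI 1.9% to 7.5%). 9/180 = 5.0%. 9/147 = 6.1%, though the protocol does not say that all nine took 600 mg. It says only that none was in the combination arm. If the four arms were equal in size and all nine were on monotherapy, the rate is 9/(0.5 × 223) = 8.1%.

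**3. Dilution.** With a share p of subjects at F and the rest at 1, the geometric mean is F^p and the arithmetic mean is 1 + p(F − 1). The median is 1.

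| p | F | Geometric mean | Arithmetic mean |
|---|---|---|---|
| 4% | 5 | 1.07 | 1.16 |
| 4% | 10 | 1.10 | 1.36 |
| 4% | 57 | 1.18 | 3.24 |
| 5% | 10 | 1.12 | 1.45 |
| 5% | 57 | 1.22 | 3.80 |
| 6.1% | 57 | 1.28 | 4.42 |

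At 8.1% the geometric mean is still only 10^0.081 = 1.21 to 57^0.081 = 1.39. Only the arithmetic mean at the extreme F approaches or passes 4.

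**4. Censoring.** If the resistant 4% are all reported as above 5, as in the SAP's example, the geometric mean is 5^0.04 = 1.07 when they enter at the bound and 1.00 when they are left out. The SAP does not say which.

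**5. Simulation with spread.** 300 subjects in one arm, 12 resistant, standard deviation of log FC 0.3 or 0.5 (assumed). The median is 1.02 to 1.03, the upper quartile 1.26 to 1.47, the arithmetic mean 1.2 to 3.7 and the maximum about 8 to 135. For F = 10 and standard deviation 0.3, the geometric mean is 1.10 with 95% CI 1.03 to 1.17. A uniform 10% shift in every subject would give the same geometric mean.

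**6. What a count shows.** In the same simulation, the number with FC above 4 averages about 9 of 300 when F = 5 and 12 to 13 when F = 10 or 57. An arm without resistance shows between 0 and about 0.8. A result of 12/300 is 4.0% (exact 95% CI 2.1% to 6.9%). Against 0/300, two-sided Fisher p = 0.0004. This assumes phenotype data for all 300 per arm; fewer will be phenotyped.

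**The case against.** **SAP 8.1 follows the protocol.** In Protocol 11.5, incidence can be read as attaching to mutations and fold change to phenotype. This stands. A reader might infer that the SAP breaks a protocol commitment, but the text does not force that. The point is that the planned summary suits the endpoint poorly.

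**Cases remain visible.** A reader might infer that the trial could appear to have no emergent phenotypic resistance. The documents do not support that. Upper-censored values are counted by arm and visit, and the SAP's own example lies above 4. Individual values are listed, and SAP 8.2 adds patient profiles combining genotype, phenotype and viral load. SAP 5.3.2 allows the range among descriptive statistics, and the maximum would stand out. All this stands, but none of it is an incidence. Quantified FC above 4 is not counted, and a censored bound need not exceed 4.

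**The most resistant isolates drop out of the means.** A reader might infer this too, but the SAP is silent on it.

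**Shifting denominators and subgroups.** SAP 2.5 defines an Endpoint record, the last visit with an EC50 or IC50 result, which eases the problem of visit-wise denominators changing as virus clears. Table 6 already applies type of SOC and baseline FC to viral phenotype. Both stand, and the fix can use them.

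**Genotype counts cover it.** They do in part. Of the nine Phase 2b subjects, seven had known PB2 mutations, one had no genotype data and one had a newly identified mutation.

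**Other documents may hold the table.** Table shells are separate (SAP 1), and resistance may be reported separately (Protocol 11.5). So the most that can be said is that the SAP text does not specify an incidence.

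**Conclusion.** The point holds for emergent (post-baseline) resistance to pimodivir. As written, SAP 8.1 gives no definition and no count of subjects crossing FC 4, so its tables supply no per-arm incidence for the phenotypic part of the endpoint. At a 4% to 5% rate with 10- to 57-fold rises, the geometric mean would be about 1.10 to 1.22 and the median about 1.0.

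These sizes are illustrations. The rate comes from Phase 2b, whose mix of background treatment differs from this trial's. The 57-fold figure is an in vitro value for M431I, which Protocol 1.1 reports from the challenge study and does not list among the emergent Phase 2b mutations. The spread of FC is assumed. The qualitative result does not depend on them: a location summary barely moves when few subjects change.

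The endpoint lies outside the confirmatory hierarchy in SAP 5.1.1 and the data are retained in listings, so no confirmatory conclusion is at risk. The change is still worth making before unblinding, because a count is the better summary of a stated endpoint and the cut-off is already in the SAP.

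**What to change.** In SAP 8.1:

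- Define treatment-emergent phenotypic resistance to pimodivir as baseline FC of 4 or below and any post-baseline FC above 4, with the Endpoint record of SAP 2.5 included.
- Count a right-censored FC as resistant when its bound is 4 or more. Report right-censored values with a lower bound as indeterminate.
- Tabulate n/N (%) by arm among subjects with paired baseline and post-baseline phenotype, overall and within the SOC subgroup already planned. Show subjects with missing baseline phenotype separately.
- Add the combined incidence by genotype and/or phenotype, as the endpoint is worded.
- Keep the FC summaries as supportive, and state how censored values enter them.
- Leave oseltamivir IC50 descriptive unless a cut-off is specified, because the documents give none.

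The cost is one definition, one phenotype table and the combined incidence. The pimodivir cut-off and the data already exist, and nothing changes at the sites.

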8.2. Viral Genotype

Assessment of viral sequences will be done to determine amino-acid substitutions that may be associated with resistance to pimodivir and to other influenza antivirals if present as part of the SOC. To that end, genotypic data for PB2, PB1, PA, NA, HA and optionally other genome segments of the influenza virus will be gathered.

All positions in the gathered regions will be analyzed for all samples, overall and by influenza subtype.

The gathered regions most relevant for pimodivir are PB2, PB1 and PA, those for neuraminidase inhibitors (NAI) (including oseltamivir) are NA and HA

The following 12 amino-acid positions in PB2 are of interest: 306, 323, 324, 325, 337, 357, 363, 376, 378, 404, 406, 431, and 510.

The following mutations in NA, associated with resistance to oseltamivir, are of interest:

- For subtype H1N1: D199N, I223R, H275Y, and N295S
- For subtype H3N2: E119V, H274Y, R292K, and N294S

The list of positions of interest might be updated during the analysis.

A mutation is treatment-emerging at a specific (post-baseline) time-point if the amino-acid of the

considered position is absent at screening/baseline and present at that timepoint.

The baseline is the collection of all polymorphisms present at any timepoint up to the first intake of study drug. A table with an overview of the time points underlying the "baseline" will be generated.

Data will be summarized using frequency tabulations (n and %). Displays and individual mutations should be presented for each genome segment separately (ie, PB1, PB2, PA, NA and HA separately). The following output will be provided:

- Baseline polymorphisms: number (%) of subjects with available genotype data, with any baseline polymorphism, and the number of subjects per polymorphism, for all polymorphisms, per treatment arm.
- Baseline polymorphisms: number (%) of subjects with any baseline polymorphism and with specific baseline polymorphisms at the positions of interest.
- Frequency tabulations for the presence of all emerging mutations overall post-baseline.
- Frequency tabulations for the presence of all emerging mutations overall post-baseline at positions of interest.
- Listing for genotype data per subject for all available timepoints including screening/baseline including viral load data (include influenza subtype and influenza subtype category). A patient profile will be created including this data supplemented with the phenotypic data.

9. PHARMACOKINETICS/PHARMACODYNAMICS

Blood samples for PK assessments of pimodivir will be collected from all subjects at the Day 3 and Day 6 visits.

Descriptive statistics of pimodivir plasma concentration over time will be tabulated for the PK analysis set.

9.1. Pharmacokinetics

Based on the individual plasma concentration-time data from all subjects, exposure parameters of pimodivir will be derived using population PK modelling. The following exposure parameters will be derived for the samples collected at Day 3 and Day 6: AUC_{12h} , C_{trough} , and, if feasible, C_{max} , and T_{max} .

Descriptive statistics, including arithmetic mean, standard deviation, geometric mean, coefficient of variation, median, minimum, maximum, and interquartile range will be calculated at Day 3 and Day 6 for all available parameters for the PK analysis set.

9.2. Pharmacokinetic/Pharmacodynamic Relationships

Pharmacokinetic/Pharmacodynamic relationships will be analyzed for the PD analysis set.

The exposure parameters AUC_{12h} and C_{trough} will be categorized into quartiles for the Day 3 visit, only C_{trough} will be categorized into quartiles for the Day 6 visit. Relationships of these parameters with the primary and selected secondary efficacy endpoints will be explored as follows.

Kaplan-Meier estimates for the time to resolution of the 7 primary influenza-related symptoms will be produced per each quartile for each exposure parameter.

The number and percentage of subjects with treatment-emergent adjudicated influenza complications will be tabulated for each quartile for each exposure parameter.

The number and percentage of subjects admitted to hospital within 28 days after treatment initiation will be tabulated for each quartile for each exposure parameter.

Kaplan-Meier estimates for the time to return to daily activities and for the time to resolution of fever will be produced per each quartile for each exposure parameter.

Relationships of AUC_{12h} with safety will be explored as follows. The number and percentage of subjects with the following treatment-emergent adverse events by AUC_{12h} quartile will be tabulated:

- Any AE
- AEs of worst grade 3 or 4
- Deaths due to AE
- Serious AEs
- AEs for which study drug was permanently stopped
- AEs at least possibly related to study drug
- Confirmed diarrhea events

A cross-tabulation of the worst treatment-emergent toxicity grades versus AUC_{12h} quartile will be presented for the laboratory parameters AST, ALT, and total bilirubin.

Separate tables will be produced for the worst treatment-emergent toxicity grades at Day 3 and overall.

10. HEALTH ECONOMICS

The following medical resource utilization data will be explored

10.1. Definitions

Measurement	Formula
Number of medical care encounters	Medical care encounters, including surgeries and other selected procedures (inpatient and outpatient), as recorded on the eCRF. The number of medical care encounters is derived as the frequency of the medical encounters other than those mandated in the protocol (eCRF).
Number of outpatient medical care encounters	Similar to the description for number of medical care encounters, but only for outpatient medical care encounters, as recorded on the eCRF (Hospital Outpatient Department, Laboratory Department, Medical Practitioner Office, Home Care).
Frequency of visits of outpatient medical care encounters	Frequency of visits will be provided per outpatient medical encounter type (Hospital Outpatient Department, Laboratory Department, Medical Practitioner Office or Home Care) as reported on the eCRF.
Type of practitioner for hospital outpatient department encounters	Type of practitioner will be provided for Hospital Outpatient Department encounters as reported on the eCRF.

